Immediately after randomization, the study staff will mail a weight scale to all participants and the additional materials (DVDs and/or USB drives, instructional handouts, GLB curriculum, Calorie King Fat & Carbohydrate Counter, and paper tracking booklets) to intervention participants. Coaches will then call participants to confirm package receipt, review materials and instructions, confirm understanding, and address any questions. Similar to the E-LITE self-directed intervention, we will deliver the intervention's core curriculum in the first 3 months using the 12-session GLB videos available via DVD, USB drive, or online streaming per Veteran preference. Veterans will also be able to choose to engage in self-monitoring of weight and activity using a web-based program (MyFitnessPal) or paper GLB booklets. A lifestyle coach will reach out every other week with messages through MyFitnessPal or text message reminding participants to watch the designated GLB video session and continue self-monitoring. We will instruct participants to contact the lifestyle coaches via MyFitnessPal messaging or phone if they have questions or would like behavioral counseling. Participants are asked to watch one ~25-minute video session a week. As recommended by guidelines, the main objective of the core curriculum (months 1-3) is to facilitate gradual weight loss through successive and progressive changes in diet and physical activity and behavioral skills training. Months 4-12 focus on continued self-directed/monitored gradual weight loss and maintenance. Participants will have access to the lifestyle coach for all 12 months of the intervention.

Self-monitoring is key to successful behavioral weight-loss interventions.⁵⁸ E-LITE results support a positive relationship between frequency of self-monitoring and weight loss.⁵⁹ We will encourage participants to continue self-monitoring through MyFitnessPal or paper trackers beyond the 3-month core intervention. The coaches will set up email reminders and text message alerts through MyFitnessPal or possibly ANNIE (does not require a smart phone).

In prior deployments of E-LITE, patients required an initial 1-hour orientation, biweekly templated messages (2 minutes/message), and ad-hoc counseling sessions 2 times per month (7 minutes/session). Based on these estimates, a 1-FTE coach could conservatively manage 450 patients over the course of a year. This centralized, off-site staffing approach is not only

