5.5 Study Evaluations

5.5.1 Baseline and follow-up effectiveness measures and data collection: Table 5 shows the study measures and data collection schedule. We have extensive experience with the requirements for administering all the measures proposed. Research coordinators may administer baseline and 3, 12, and 21-month follow-up surveys via telephone, record responses

on paper, or Qualtrics, and enter values into study databases using double data entry and logic controls to minimize error. To emulate paper surveys and study staff calling after review, Qualtrics will prompt participants to respond to questions if they accidentally left them blank. Furthermore, personalized survey completion messages will be incorporated into Qualtrics to direct participants to the next action. Other slight modifications (e.g., bolded fonts, transition pages, and sub-headers) of Qualtrics can be accounted by the formatting appeal of the online interface. We will assess information using a health inventory checklist including socio-demographic characteristics, health behaviors, global impression of change, and non-VA weight loss programs. We will obtain additional information about comorbid conditions, medication use, healthcare utilization, and distance to clinics from the CDW. We will compensate participants \$25 if they complete the 12-month packet in the follow-up window and an additional \$25 at the end of 21-month follow-up period if they completed 3,12 (if not already compensated), or 21-month outcome surveys.

Table 5: Measures and timing of collection

Variable	Source	B	3m	12m	21-24m
Baseline variables and covariates					
Height	EMR	X			
Clinical AHI	Chart review (JLV, CAPRI)	X			
Demographics	Self-report	X			
Non-VA weight loss program	Self-report	X	X	X	X
Adherence to Intervention	Survey		X	X	
Outcomes					
Primary Effectiveness Outcomes					
Sleep-related quality of life (FOSQ)	Surveys	X		X	
Weight (clinical)	CDW	X		X	
Secondary Effectiveness Outcomes					
Cardiovascular Risk Score	CDW	X		X	X
Weight (Clinical)	CDW	X	X		X
Weight (Self-report)*	Survey		X	X	X
FOSQ	Survey	X	X		X
Blood Pressure	CDW	X		X	X
Global Impression of Change	Survey		X	X	X
Sleep Symptoms	Survey	X	X	X	X
Well-Being	Survey	X	X	X	X
Objective PAP adherence	Remote Downloads	X	X	X	X
Self-reported adherence to sleep apnea treatments	Survey	X	X	X	X
Sleep Duration	Survey	X	X	X	X

Research AHI**	HSAT				X	

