6.0 Reporting

6.1 Quality monitoring

The investigators will closely monitor and prepare annual summary reports on:

- Patient accrual and follow-up completion/retention in relation to goals and timeline.
- Randomization process and group comparability on the balancing variables.
- Key baseline characteristics of the sample, by blinded group, on the primary and secondary outcome variables.
- Intervention adherence.
- Protocol violations.

6.2 Data Safety and Monitoring Board.

This study will be reviewed regularly (at least annually) by a DSMB convened by the national director of VA HSR&D. This board will monitor the quality of data, progress of recruitment, as well as the incidence of adverse events between arms.

6.3.1. Adverse event monitoring.

To ensure unbiased determination across treatment arms, at 12- and 21-month follow-up contact we will ask participants to complete a survey about potential adverse events (AE), serious adverse events (SAE) and unanticipated problems (UP) employing a body system-based assessment. We define SAEs as those requiring hospitalization or death.

Study staff will collect adverse events using participant self-reports collected at 12 and 21 months. Study staff will also perform chart reviews looking for discharge summaries for the 12 month time period. Study staff will later complete additional chart reviews looking for discharge

summaries for the 21 month time period among patients who do not complete 21 month surveys. [name] or another clinician will assess each AE for duration (start and stop dates and times), expectedness in the study population, severity, outcome, treatment, and relation to study activity.

To account for potential differential survey response rates by arm, we will also query the electronic medical record and compile hospital admissions from randomization through 24 months post randomization. We will report the number of hospitalizations by arm to in our final DSMB report.

The following are expected adverse events in the POWER population of participants who have obstructive sleep apnea, a high BMI, and adopt healthy eating and physical activity program:

- Gastrointestinal symptoms related to change in diet.
- Musculoskeletal symptoms or injury resulting from increased physical activity, including increasing symptoms such as chest discomfort, shortness of breath, and leg cramping.

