5. Plans for any interim analysis of the data:

We do not plan to perform any interim analyses for superiority, futility, or sample size re-estimation. The D-ELITE weight loss intervention is consistent with existing VA guideline-based care for obesity and obstructive sleep apnea. Our trial is therefore meant to promote recommended medical care, and we do not believe an interim analysis of the data is warranted.

6. Missing and Misclassified Data:

For our primary outcomes, we assume 20% attrition to retain power of 0.9. However, we expect to retain sufficient power, 0.8, even if we experience dropout of over 39% (Table 1). Our pragmatic trial prioritizes outcome collection from EMR, including JLV and CAPRI, to reduce participant burden and enhance generalizability. While we attempt to minimize missingness and misclassification through efforts to optimize follow up survey completion and validated approaches to decrease measurement error, we anticipate missing data. We originally considered complete case analyses, but ultimately chose an approach based on linear mixed models and maximum likelihood that is valid under the missing at random assumption. Linear mixed models impute missing outcome data implicitly within a hierarchical model, using

individuals' baseline, adjustment, and stratification values. Missing values of covariates will be imputed using the chained equations approach (e.g. MICE), using single imputation if missing rates are less than 5% and multiple imputation otherwise. We will carry out the recommended sensitivity analyses to the MAR assumption using methods based on pattern mixture models and imputation, by assuming a range of perturbations of imputed outcome values and assessing differences in model conclusions.

Table 1. Change in Functional Outcomes of Sleep Questionnaire (FOSQ)

Power	Alpha	SD (score)	Difference (score)	N	Attrition (%)
0.90	0.025	2.5	0.75	556	20
0.80	0.025	2.5	0.75	426	39
Change in Clinically Measured Weight					
Power	Alpha	SD (kg)	Difference (kg)	N	Attrition (%)
0.99	0.025	6.9	3.3	556	20
0.90	0.025	6.9	3.3	220	68
0.80	0.025	6.9	3.3	170	76
0.90	0.025	6.9	2.1	556	20

7. List and definitions of covariates to be included in models:

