which models for each patient i their measure for each outcome (FOSQ and weight separately), incorporating time of measurement T_j (0 or 12 months), treatment by time interaction $X_i T_j$, stratification variables Q_i , and adjustment variables A_i including age, gender, race, Charlson comorbidity index, and rurality. The model will include a random normal intercept u_i for each patient and a random normal error term ϵ_{ij} , all assumed independent. The variances of the ϵ_{ij} will be assumed different at baseline and 12 months. Here, β_0 is the average baseline FOSQ/weight among the control and treatment groups combined (assumed equal due to randomization), β_1 is the expected change in FOSQ/weight over time in the control group, and β_2 , the quantity of interest in hypothesis H1, is the expected difference in the change in FOSQ/weight over time between the treatment and control groups, or equivalently the expected difference between groups at 12 months. In secondary analyses, we will incorporate primary and secondary outcomes from each time point (baseline, 3, 12, and 21 months). We will use the same model to test secondary outcomes captured only at follow up, omitting baseline values.

Additional Analytic Subgroups: In addition to analyses of the entire sample using intent to treat, we will analyze primary and secondary outcomes according to model 1 and model 2 in the following groups:

- 1) Subgroups defined by each of the three pre-specified strata (see section 4).
- 2) Subgroups defined by gender.
- 3) Patients who are prescribed continuous positive airway pressure and use <4 hours per night in the 90 days before the outcome period.
- 4) The subgroup of patients who are prescribed continuous positive airway pressure and use ≥ 4 hours per night in the 90 days before the outcome period.

10. Adverse and Serious Adverse Event Monitoring:

To ensure unbiased determination across arms at 12- and 21-month follow-up, we will ask participants to complete a survey about potential adverse events (AE), serious adverse events (SAE) and unanticipated problems (UP) employing a body system-based assessment. We define SAEs as those resulting in hospitalization or death.

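### Cheap improvement, not an error: the primary model uses only baseline and 12-month values, so participants missing at 12 months add almost nothing, although 3-month FOSQ is already scheduled

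*SAP*

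**What the plan says.** SAP section 9 and Protocol 5.6.2 give the same H1 model for FOSQ and weight. Time takes two values (the definition reads "0 or 12 months), treatment by time interaction"). Both arms share one baseline mean. There is a random patient intercept, a separate residual variance at each visit, and fixed terms for the stratification and adjustment variables. The treatment effect is beta2. Visits at 3 and 21 months enter only through one sentence: "In secondary analyses, we will incorporate primary and secondary outcomes from each time point (baseline, 3, 12, and 21 months").

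SAP section 6 and Protocol 5.6.3 explain that this model replaced complete-case analysis because it is valid under missing at random (MAR). They say it implicitly imputes missing outcomes from "baseline, adjustment, and stratification values". Two further provisions deserve credit: "Missing values of covariates will be imputed using the chained equations approach", and "We will carry out the recommended sensitivity analyses to the MAR assumption using methods based on pattern mixture models and imputation".

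Three-month data are already planned. Protocol 5.5.1 states: "Research coordinators may administer baseline and 3, 12, and 21-month follow-up surveys via telephone". Table 5 there marks both FOSQ (survey) and clinical weight (CDW) at 3 months, as secondary outcomes.

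**The concern.** A mixed model protects better than complete-case analysis when it brings in extra outcome information on people who later go missing. With two visits the only outcome value left for such a person is the baseline, which an ANCOVA conditions on anyway. The primary analysis is therefore protected if a missing 12-month value depends on arm, baseline and the listed covariates. It is not protected if missingness also depends on how the person was doing at 3 months, and does so differently by arm. The 3-month FOSQ is the scheduled measurement that speaks to this, and it is left out of the primary test. At stake is possible bias in a co-primary estimate when 20% attrition is assumed.

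**Working it through.** **Inputs from the plan.** 696 randomised 1:1; two-sided alpha 0.025 per outcome; 20% attrition; FOSQ difference 0.75, SD of change 2.5; weight difference 3.3 kg, SD 6.9 kg (SAP sections 2 and 6, Protocol 5.6.1).

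**The plan's own figures reproduce.** The exact two-sample t-test gives N = 556 for 0.90 power and 426 for 0.80 on FOSQ, as stated; 556/0.8 = 695, or 348 per arm, hence 696. For 3.3 kg at N = 556, power is above 0.999. These figures count completers, so this point does not touch them.

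**Why non-completers add nothing.** A random intercept plus two residual variances gives three parameters for a 2×2 covariance, so the covariance is unrestricted. With a common baseline mean and no covariates,

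E[Y12 | Y0, X] = beta0 + beta1 + beta2·X + g·(Y0 − beta0).

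The likelihood factors into a baseline part and this regression, and beta2 appears only in the regression, which is fitted to completers. Checks:
- Without covariates, the variance of beta2 using all participants divided by that using completers is 1.00000.
- With eight covariates whose coefficients are shared across visits, the ratio is 0.9991–0.9999 at 20% missing and 0.9977–0.9997 at 39%: a gain of at most 0.23%.

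**Possible bias, FOSQ.** The documents give no dropout mechanism and no 3-month completion rate, so the following are assumptions: 20% missing per arm; in the intervention arm only, odds of missing multiplied by 1.5 to 2.0 per SD worse 3-month change; correlation r of 3- and 12-month change 0.5 to 0.7; 3-month effect 60% of the 12-month effect. If change is unrelated to baseline,

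bias = r × 2.5 × m, with m = −E[z·p(z)]/0.8.

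Here z is the standardised 3-month change and p(z) the logistic probability of missing, averaging 0.20. Numerically, m = 0.079 (odds ratio 1.5) or 0.129 (2.0).
- Low end: 0.5 × 2.5 × 0.079 = 0.10.
- High end: 0.7 × 2.5 × 0.129 = 0.23.

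Large-sample simulation (true 0.75):

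| One-arm dependence on 3-month change | FOSQ estimate |
|---|---|
| Two visits, change unrelated to baseline | 0.84–0.98 |
| Two visits, equal SD at every visit (baseline SD 3 assumed) | 0.81–0.93 |
| Three visits, all non-responders have a 3-month value | 0.74–0.76 |
| Three visits, half have one | 0.78–0.85 |
| Three visits, 20% have one | 0.80–0.92 |

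The standard error is 2.5 × sqrt(4/556) = 0.21, so +0.06 to +0.23 is about 0.3 to 1.1 standard errors. With the same dependence in both arms, the two-visit estimate is 0.72–0.75.

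**If missingness follows the 12-month change itself** (one arm, change unrelated to baseline), two visits give 0.94–1.09. Three visits remove about 24–51% of the bias with full 3-month data, 13–27% with half, and 5–11% with 20%.

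**Precision only.** If missingness is unrelated to response, with d missing at 12 months, share q of those having a 3-month value, and r now the 3-to-12-month correlation given baseline,

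variance ratio = (1 − r²) + r²(1 − d)/[(1 − d) + d·q].

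With d = 0.2, q = 0.5, r = 0.6: 0.64 + 0.36 × 0.8/0.9 = 0.96. FOSQ power rises from 0.903 to 0.915 (normal approximation). Over r = 0.5–0.7 and q = 0.2–1, the standard error falls by about 0.4–5%; the low end also allows for 3-month values missing among completers.

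**Why unstructured covariance.** Keeping one random intercept with independent residuals over three visits, with full 3-month data and one-arm dependence, gives 0.75–0.84 against 0.74–0.76 unstructured.

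**The case against.** The strongest reply is that nothing is wrong. The plan claims validity under MAR and imputation from baseline and covariates, and both claims are accurate. An all-visit analysis and a pattern-mixture sensitivity analysis are already planned. What remains is which of two MAR models is called primary. This stands, and it is why the point is an improvement and not an error. But neither planned analysis is the H1 test, and the sentence on the all-visit analysis gives no time coding, no covariance for more than two visits and no target contrast.

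A reader might infer that the documents foresee the harmful dropout. Protocol 6.3.1 does say "To account for potential differential survey response rates by arm", but that concerns survey response rates in adverse-event collection. A rate difference by arm alone does not bias beta2, because arm is in the model; missingness must also follow response, differently by arm. Nor does coach access settle it (Protocol 5.3.6.2: "Participants will have access to the lifestyle coach for all 12 months of the intervention"): research coordinators, not coaches, administer the surveys by telephone.

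A reader might also infer that the all-visit analysis would misstate the 12-month contrast by treating time as linear. The SAP does not say that time is linear, and that analysis is secondary, so this shows no defect in H1.

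The illustration also favours the remedy, because the missingness is generated from the 3-month value. When it follows the 12-month value, the gain is only partial, and the pattern-mixture analysis is the planned tool for that case.

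For weight the objection largely succeeds. Three-month clinic weights are opportunistic and have no stated window, and the request to schedule a weight visit covers 12 months only (Protocol 5.5.2). A window as wide as the 12-month one (±3 months) would span 0 to 6 months. SAP section 3 and Protocol 5.5.2 also provide for substituting self-collected weights in sensitivity analyses. A 12-month self-weight is a more direct remedy than a 3-month value; Protocol 2.5.7 reports a correlation of 0.94 with clinic weights.

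**Conclusion.** The point holds as a cheap improvement for FOSQ. It is certain that H1 uses two visits, that participants without a 12-month value add essentially nothing to beta2, and that 3-month FOSQ is scheduled but unused in the primary test. The consequence is conditional. Bias of about +0.06 to +0.23 points arises only under assumed one-arm dropout that follows 3-month response. Adding the 3-month visit takes it to near zero with full 3-month data, and removes only part of it if few non-responders have a 3-month score or if missingness follows the 12-month value. With equal dependence in both arms there is almost no bias to remove. If missingness is unrelated to response, the gain is a standard error about 0.4–5% smaller. The documents do not show which case will apply.

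For weight, the case supports a sensitivity analysis and no change to the primary model.

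**What to change.** **FOSQ.** In SAP section 9 and Protocol 5.6.2, fit H1 to baseline, 3 and 12 months, with time as a factor, arm-by-time terms, a common baseline mean and an unstructured covariance. Test the same 12-month contrast at alpha 0.025. Keep the two-visit model and the pattern-mixture analyses as sensitivity analyses. Report by arm how many 12-month non-responders have a 3-month score. Make and date the change before outcomes are analysed. The Protocol abstract says analysis has not begun; confirm that this is still so. If outcomes have been analysed, keep the current primary model and name this three-visit model as the key sensitivity analysis.

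**Weight.** Keep the two-visit primary model. Add the three-visit model as a sensitivity analysis with a stated 3-month window, alongside the self-weight substitution already planned.

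**Cost.** Wording, programming and one weight window; no new data collection. The real downside is a further change to the primary FOSQ model after the switch from ANCOVA (SAP version 3.1, Protocol version 2.10), which was made while 12-month outcomes were being collected. The dated record must therefore show that the change came before any outcome analysis.

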$$Y_{ii} = \beta_0 + \beta_1 T_i + \beta_2 X_i T_i + \beta_3 Q_i + \beta_4 A_i + u_i + \epsilon_{ii}$$

which models for each patient i their measure for each outcome (FOSQ and weight separately), incorporating time of measurement T_j (0 or 12 months), treatment by time interaction $X_i T_j$, stratification variables Q_i , and adjustment variables A_i including age, gender, race, Charlson comorbidity index, and rurality. The model will include a random normal intercept u_i for each patient and a random normal error term ϵ_{ij} , all assumed independent. The variances of the ϵ_{ij} will be assumed different at baseline and 12 months. Here, β_0 is the average baseline FOSQ/weight among the control and treatment groups combined (assumed equal due to randomization), β_1 is the expected change in FOSQ/weight over time in the control group, and β_2 , the quantity of interest in hypothesis H1, is the expected difference in the change in FOSQ/weight over time between the treatment and control groups, or equivalently the expected difference between groups at 12 months. In secondary analyses, we will incorporate primary and secondary outcomes from each time point (baseline, 3, 12, and 21 months). We will use the same model to test secondary outcomes captured only at follow up, omitting baseline values.

Additional Analytic Subgroups:

- 1) Subgroups defined by each of the pre-specified strata.
- 2) Subgroups defined by gender.
- 3) Patients who are prescribed continuous positive airway pressure and use <4 hours per night in the 90 days before the outcome period
- 4) The subgroup of patients who are prescribed continuous positive airway pressure and use ≥4 hours per night in the 90 days before the outcome period.

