Methodology: We plan a hybrid type 1 pragmatic randomized controlled trial. We will proactively identify Veterans with OSA and obesity nationwide using data from the CDW (n=696), randomizing 1:1 to usual care plus the D-ELITE weight loss intervention or usual care alone. We will collect primary outcomes at 12-months, but we will also collect outcomes at 3- and 24-months to assess trends over time. For our implementation process evaluation, we will use quantitative and qualitative methods to assess barriers to implementation, including a comprehensive budget impact analysis.

2. Sample Size Rationale:

We designed this pragmatic trial to achieve power of 0.9 for two primary outcomes at 12 months assuming 20% attrition using a two-sample t-test of independent means (STATA version 16.1). We target a two-sided type I alpha of 0.025 for each outcome to account for a Bonferroni correction. FOSQ: We plan to detect an established meaningful and important difference for FOSQ between groups, 0.75 points, and assume the known standard deviation for change in FOSQ of 2.5 points. Weight: Participants in a prior version of the D-ELITE self-directed intervention lost 4.5 kg. Assuming weight loss in our comparator group is similar to average Veterans with OSA seeking weight loss, 1.2 kg, we expect a 3.3 kg difference between groups. This difference approximates a meaningful difference of 3% weight loss ([name] et. al., JAMA, 2022. PMID: 36511927). Given known standard deviation in clinical weight change among Veterans' attempting weight loss of 6.9 kg/year, we will have 0.99 power to detect this 3.3 kg

difference in weight change with 20% attrition (Table 1). We will detect a 2.1 kg difference with power of 0.90. Across both co-primary outcomes, we retain power of 0.8 even with 39% or more attrition (Table 1).

3. Description of how data will be collected:

We will enroll 696 Veterans nationwide. In CDW, we will identify Veterans with an eligible outpatient BMI and sleep study recorded in the past 6 months with associated diagnosis of OSA who are free from exclusionary conditions searchable in CDW.

- **Research invitation:** We will invite potentially eligible patients by mail and email, and will send an invitation letter, information statement, and an opt-in/out postcard and Qualtrics link.

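### Subgroup effects are to be estimated level by level with no treatment-by-subgroup test, so a uniform effect, on FOSQ above all, could readily look different between subgroups

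*SAP*

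**What the plan says.** SAP section 9, under Additional Analytic Subgroups, says that "we will analyze primary and secondary outcomes according to model 1 and model 2 in the following groups". The groups are the levels of the three stratifiers (BMI category, OSA severity, sleep-related impairment), gender, and two groups of patients prescribed CPAP, divided by nightly use in the 90 days before the outcome period. Protocol 5.6.2 gives the same list, starting with "Subgroups defined by each of the pre-specified strata", but states no method.

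The SAP prints one unnumbered mixed model, so the two numbered models in the sentence above are not defined in the current text. In the printed model the stratifiers and gender are main effects, and treatment enters only through its interaction with time.

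Neither document gives a treatment-by-subgroup term, an interaction test, an alpha for subgroups or a rule for interpreting them. SAP section 2 addresses the overall comparison only: "We designed this pragmatic trial to achieve power of 0.9 for two primary outcomes at 12 months assuming 20% attrition", with "We target a two-sided type I alpha of 0.025 for each outcome to account for a Bonferroni correction".

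**The concern.** The natural reading of the SAP sentence is that the model is refitted within each level. Each fit asks whether there is an effect in that level. None asks whether the effect differs between levels, which is the question a subgroup analysis is meant to answer. A trial with 0.90 power overall has much less in each half, so one significant and one non-significant level is a common result even when the true effect is identical.

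This could have practical consequences. Protocol 5.5.6.3 and 5.6.4 allow for budget-impact sensitivity analyses by subgroup or for more targeted roll-out. Protocol 5.2.4 sets a goal of about 30% women. Because women would be the smaller group, the likeliest spurious pattern is an effect in men and none in women.

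**Working it through.** **Inputs.** From SAP section 2 and SAP Table 1: 556 analysed, 1:1, so 278 per arm. The FOSQ difference is "0.75 points, and assume the known standard deviation for change in FOSQ of 2.5 points". For weight, "we expect a 3.3 kg difference between groups"; also "We will detect a 2.1 kg difference with power of 0.90"; the SD is that for Veterans "attempting weight loss of 6.9 kg/year". No subgroup alpha is given, so 0.025 and 0.05 are both shown. Assumed: 50:50 for each stratifier (the SAP's summary of edits records an expectation of roughly even categories), 30:70 for gender (Protocol 5.2.4), and equal attrition and SD in every level.

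**Step 1, the plan's own figure.** Power = Φ(δ / (SD·√(2/n)) − z), with n per arm and z = 2.241 at alpha 0.025. For FOSQ with n = 278: 0.75 / (2.5·√(2/278)) = 3.537, and Φ(3.537 − 2.241) = 0.902. SAP Table 1 states 0.90.

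**Step 2, power within levels under one uniform FOSQ effect.**
- 50:50 factor, n = 139: Φ(2.501 − 2.241) = 0.602 in each level.
- Women, n = 0.3 × 278 = 83.4: Φ(1.937 − 2.241) = 0.381.
- Men, n = 0.7 × 278 = 194.6: Φ(2.959 − 2.241) = 0.764.

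**Step 3, chance that exactly one level is significant.** The levels contain different patients, so this is p1(1 − p2) + p2(1 − p1).
- 50:50: 2 × 0.602 × 0.398 = 0.479.
- Gender: 0.381 × 0.236 + 0.764 × 0.619 = 0.090 + 0.473 = 0.563. The second part, 47%, is significant in men only.

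| Uniform effect | Split | Power by level (alpha 0.025) | Exactly one significant, alpha 0.025 | alpha 0.05 |
|---|---|---|---|---|
| FOSQ 0.75 | 50:50 | 0.60, 0.60 | 48% | 42% |
| FOSQ 0.75 | 30:70 | 0.38, 0.76 | 56% | 51% |
| Weight 2.1 kg | 50:50 | 0.62, 0.62 | 47% | 41% |
| Weight 2.1 kg | 30:70 | 0.39, 0.78 | 56% | 50% |
| Weight 3.3 kg | 50:50 | 0.96, 0.96 | 8% | 4% |
| Weight 3.3 kg | 30:70 | 0.80, 0.99 | 20–21% | 13–14% |

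The non-central t gives the same results to within about one percentage point; the ranges in the last row span the two methods. At the roughly 25% women that Protocol 5.2.4 reports part-way through recruitment, the FOSQ gender figure is 61% (56% at alpha 0.05).

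**Step 4, allowing for baseline adjustment.** The printed model assumes a common baseline mean and lets residual variances differ between visits, so in effect it adjusts for baseline. With equal variances and baseline-to-12-month correlation ρ, the SD of 2.5 is multiplied by √((1 + ρ)/2). The documents give no ρ. For an assumed 0.5 to 0.8 the SD is 2.17 to 2.37, and the FOSQ split rates (non-central t) become:
- 50:50: 39–46% at alpha 0.025, 29–38% at 0.05.
- Gender 30:70: 51–55% at alpha 0.025, 41–48% at 0.05.

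**Step 5, comparison with an interaction test.** Under a uniform effect, an interaction test signals a difference at its nominal rate, 2.5% or 5% per factor. Its power is low. If the whole 0.75 effect sat in one half, the SE is 2.5·√(2/139 + 2/139) = 0.424, and power is Φ(0.75/0.424 − 2.241) = Φ(−0.473) = 0.32. For gender at 30:70 it is 0.27.

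**Step 6, all four baseline factors.** A simulation of 6,000 trials with independent factors and no baseline adjustment gave at least one split on FOSQ in 82% of trials (76% at alpha 0.05). For weight at 3.3 kg the figure was 30% (19%). At least one false interaction signal on FOSQ arose in about 10% (19%).

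**The case against.** Four objections have force.

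- **Weight.** The SAP expects 3.3 kg; 2.1 kg is only the difference detectable at 0.90 power. At 3.3 kg splits are uncommon for balanced factors and moderate for gender. This stands, so the case rests mainly on FOSQ.
- **The change-score calculation overstates the rates.** It does, because the mixed model uses baseline. Step 4 shows that the reduction is limited over the assumed correlations, and what remains is still material.
- **A split in p-values is not a false claim.** A reader might infer from the 48%, 56% or 82% that the trial will probably report false subgroup differences. The documents do not support that. H1, H2a and H2b contain no subgroup hypothesis, the subgroups are listed as additional analyses, and nothing says that p-values will be compared between levels. What stands is that within-level results are the only subgroup results planned, and no rule prevents that comparison.
- **Roll-out.** A reader might also infer that a national programme would be misdirected. The main budget projection covers all VA patients with both conditions; targeted strategies are only a possible sensitivity analysis. Spurious differences could feed that analysis, but no more than that is shown.

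Protocol 5.6.2 states no method, so the evidence for level-by-level fitting comes from the SAP alone.

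**Conclusion.** The point holds for the three stratifiers and gender. The omission is clear in both documents. Its consequence is conditional: false subgroup differences could readily be reported, mainly for FOSQ, if within-level significance is taken as evidence of a different effect.

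Under a uniform 0.75-point effect the FOSQ split rate is 48% for a balanced factor and 56% for gender at alpha 0.025 (42% and 51% at 0.05). With baseline adjustment it is 29–46% and 41–55% across both alphas. For weight it is similar at 2.1 kg, but 4–8% and 13–21% at the expected 3.3 kg. These figures rest on the assumed splits, equal SD and attrition across levels, and the assumed correlation.

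The two CPAP-use groups raise a different problem. They are formed after randomisation and only among patients prescribed CPAP, so an interaction term would not make those comparisons randomised. The primary analysis is unaffected.

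**What to change.** Revise SAP section 9, with matching text in Protocol 5.6.2:

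- For BMI category, OSA severity, sleep-related impairment and gender, fit one full-sample model per factor: the printed model plus subgroup-by-time and treatment-by-time-by-subgroup terms.
- Report the three-way estimate with its 95% CI as the exploratory evidence that the effect differs. Show within-level estimates from the same model as descriptive only.
- Keep the CPAP-use groups out of this scheme and label them as non-randomised descriptive comparisons.
- Replace the reference to two numbered models with a reference to the model that the SAP prints.

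No new data are needed; the cost is one SAP paragraph and the matching protocol text. The downside is the low interaction power shown in Step 5, about 32% even in an extreme case for a balanced factor, so fewer subgroup claims will be possible. That is a reason to label the analysis exploratory and rely on the interval, not to leave the test out.
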